10.6 Handling of missing infusion durations

If the start time or end time of the infusion or the time point of the infusion rate increase is missing, study treatment administration times as stipulated in the protocol will be assumed for analysis, i.e., 15 min duration of the initial infusion rate and 72 min of the increased infusion rate.

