5.1.4 Study treatment administration

The following infusion scheme is to be followed:

- Start with an infusion rate of 20 mL/h (0.333 mL/min) for 15 min for the first 5 mL.
- Increase infusion rate to 37.5 mL/h (0.625 mL/min) for 72 min for infusion of the remaining 45 mL.

Note: A dedicated infusion line must be used for i.v. selexipag administration. No other drugs or solutions should be administered through this line.

The following information will be collected in the CRF to document each i.v. selexipag administration:

- Date of administration.
- Concentration of the i.v. infusion solution.
- For each infusion rate: clock time of start and end.

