5.5.1.4 Study treatment adjustments or interruptions, end of infusion status

Incidence of and reasons for i.v. administration interruption as well as the end of infusion status (irrespective of whether study treatment was completed as per protocol or not) will be summarized for each of three infusions.

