5.5.2 Compliance with study treatment

Compliance with i.v. selexipag treatment is defined as the percentage of the actual dose infused compared with the planned dose to be infused, for each infusion and overall.

The planned dose to be infused will be determined from [Table 6](#) below and based on the subjects' stable Uptravi dose taken from the Visit 2 Day 1 evening dose.

Table 6 Correspondence of i.v. selexipag dose compared to Uptravi oral doses

Uptravi oral dose (μg)	Corresponding i.v. selexipag dose (μg)
200	225
400	450
600	675
800	900
1000	1125
1200	1350
1400	1575
1600	1800

The actual infused dose will be computed by computing the product of the infusion rate (mL/h) with the concentration of infusion solution (μg/mL) as recorded in the eCRF and the elapsed time between start and end time (h) for each infusion to obtain the amount of i.v. selexipag infused.

Missed infusions will be entered with 0 μg actual infusion into the compliance analysis.

The planned dose, actual dose, and resulting compliance will be listed. Compliance will be summarized descriptively for each period and overall.

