7.8.3.1 Dose normalization

Dose normalization will be conducted to the lowest prescribed selexipag dose (200 µg for oral Uptravi and 225 µg for i.v. selexipag).

Dose normalized plasma concentrations, $C_{\text{trough, ss, norm}}$, $C_{\text{max, ss, norm}}$ and $AUC_{\tau, ss, \text{norm}}$ will be determined by dividing the respective parameters by the actual dose and multiplying with 200 or 225 for Uptravi and i.v. selexipag parameters, respectively.

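### SAP 10.6 imputes the full infusion duration whether or not the infusion was completed, so a partial infusion with a missing time is booked at 100% of planned dose

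*SAP*

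**What the plan says.** SAP 10.6 is triggered as follows: "If the start time or end time of the infusion or the time point of the infusion rate increase is missing". In that event "study treatment administration times as stipulated in the protocol will be assumed for analysis", namely "15 min duration of the initial infusion rate and 72 min of the increased infusion rate". One missing time out of the three is enough, and the section does not mention how the infusion ended.

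SAP 5.5.2 computes the actual dose as infusion rate × recorded concentration × "the elapsed time between start and end time (h) for each infusion". Compliance is actual over planned dose, per infusion and overall. The only rule for non-delivery is that a missed infusion counts as 0 µg; a partly delivered infusion is not addressed.

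The infusion scheme in Protocol 5.1.4 is "Start with an infusion rate of 20 mL/h (0.333 mL/min) for 15 min for the first 5 mL", then "Increase infusion rate to 37.5 mL/h (0.625 mL/min) for 72 min for infusion of the remaining 45 mL". Protocol 5.1.8.2 treats compliance outside 80% to 120% over the whole treatment period as a protocol deviation.

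SAP 5.5.1.4 separately summarises "the end of infusion status (irrespective of whether study treatment was completed as per protocol or not"), for each infusion. Its mock table (T_EXP_ADJ) has rows for temporary interruption, premature discontinuation and completion. SAP 7.8.3.1 normalises the PK parameters "by dividing the respective parameters by the actual dose".

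**The concern.** The imputation suits an infusion known to have run to completion with a time left blank. It does not suit one known to have stopped early, because it supplies exactly the quantity that was cut short. The documents foresee such stops: Protocol 5.1.11 lists events that end i.v. treatment, and the mock table and mock dosing listing both provide for interruption due to an AE.

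The exposure and compliance tables are at stake. Under Protocol 5.1.10 a subject counts as having prematurely discontinued only if the third infusion was not initiated, so a third infusion that starts and then stops falls outside that definition. Actual dose and compliance are then among the few outputs that would measure the shortfall. Under 10.6 they could show 100% for an infusion that another table reports as stopped.

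The literal trigger goes further. If start and end are both recorded and only the rate-change time is missing, the recorded end time is still replaced.

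**Working it through.** **Inputs.** Rates and durations: Protocol 5.1.4 and SAP 10.6. Dose and compliance formulas: SAP 5.5.2. Planned doses of 225 to 1800 µg: SAP Table 6. The 80% limit: Protocol 5.1.8.2. The stop times are my assumptions, since the documents give none.

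**Step 1: reproduce the plan's figures.**
- Volume: 20 mL/h × 15/60 h = 5 mL; 37.5 mL/h × 72/60 h = 45 mL; total 50 mL in 87 min.
- Concentration: 1800 µg / 50 mL = 36 µg/mL, which agrees with Protocol 1.2.3. At the lowest dose, 225 / 50 = 4.5 µg/mL.
- Overall compliance in the mock listing: (850 + 870 + 900) / (3 × 900) = 2620 / 2700 = 97.0%, as shown there. Overall compliance is therefore total actual over total planned dose.

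**Step 2: what the rule books.** The imputed times at protocol rates give 50 mL. With the correct concentration this equals the planned dose at every level, so the affected infusion has 100% compliance whatever was delivered.

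**Step 3: what was delivered.** For a stop at t minutes, from 15 to 87:

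V(t) = 5 + 37.5 × (t − 15)/60 mL; infusion compliance c = V(t)/50.

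If the other two infusions were complete, overall compliance = (100% + 100% + c)/3.

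| Assumed stop (min) | V (mL) | True c | Booked c | True overall | Booked overall |
|---|---|---|---|---|---|
| 15 | 5.00 | 10.0% | 100% | 70.0% | 100% |
| 25 | 11.25 | 22.5% | 100% | 74.2% | 100% |
| 39 | 20.00 | 40.0% | 100% | 80.0% | 100% |
| 60 | 33.125 | 66.25% | 100% | 88.75% | 100% |
| 75 | 42.50 | 85.0% | 100% | 95.0% | 100% |

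At 1800 µg, the 25-min row means 11.25 × 36 = 405 µg delivered and 1800 µg booked.

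**Step 4: the deviation limit.** (200% + c)/3 = 80% gives c = 40%, so V = 20 mL and t = 15 + (20 − 5)/0.625 = 39 min. A third infusion stopped before 39 min is truly below 80% overall but is booked at 100%.

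The masking depends on the other infusions being complete. If the second infusion stops at 25 min and the third is missed, the true value is (100 + 22.5 + 0)/3 = 40.8% and the booked value (100 + 100 + 0)/3 = 66.7%. The figure is wrong, but both values breach the limit.

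**Step 5: the literal override.** Suppose start and end are recorded 39 min apart and only the rate-change time is missing. Placing the rate change at 15 min uses all the recorded data: 5 + 37.5 × 24/60 = 20 mL, or 40%. SAP 10.6 as written gives 50 mL, or 100%.

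**The case against.** The strongest reply is that this may never happen. Protocol 5.1.4 collects clock times of start and end for each infusion rate, infusions are given in hospital by site personnel, and Protocol 11.3 provides programmed queries. With about 18 subjects there are some 18 × 3 = 54 infusions, and the error needs both a missing time and an incomplete delivery. An interrupted infusion that was resumed and fully delivered would be booked correctly. Compliance is descriptive, and SAP 10.4 defers derivation detail to a programming specification that is not available here. All of this stands and keeps the point minor. It does not remove the rule as the SAP states it.

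Three stronger readings are tempting, and the documents do not support them.

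- *The rule hides early stops.* The stop would still appear in the end-of-infusion table and in the dosing listing, with its reason. The result is a contradiction between outputs, not concealment.
- *Missing times cluster in infusions interrupted for an event.* Nothing in the documents says so, and the mock dosing listing gives each infusion segment its own start, end and reason.
- *Dose-normalised AUC would be 4.4 times too low.* The factor is 50/11.25 for the assumed 25-min stop, and it needs three conditions.
  - The third infusion must be the partial one, since i.v. PK sampling is on Day 3. A first or second infusion stopped under Protocol 5.1.11 is not followed by a third, and the PKS requires all three.
  - The actual dose in SAP 7.8.3.1 must mean the computed infused dose. That section does not cite 5.5.2, and the power model in SAP 8.2.2.3 uses the scheduled dose.
  - The subject must remain in the PKS. If deviation code 323 in SAP Table 3 covers infused dose, a 25-min stop at 1800 µg (1800 − 405 = 1395 µg short) exceeds its 225 µg margin and excludes the subject.

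  Even then, dividing by the true dose would not give a clean value, because the Day 3 profile includes carry-over from earlier infusions.

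**Conclusion.** The point holds for exposure and compliance. SAP 10.6 has no condition on completion, and SAP 5.5.2 turns its imputed times into the full planned dose. For the assumed stops from 15 to 75 min, an infusion that delivered 10% to 85% is booked at 100%. If only the third infusion is affected, overall compliance is overstated by 5 to 30 percentage points, and a stop before 39 min passes the 80% check wrongly.

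This rests on the correct concentration being recorded, at least one of the three times being missing, and the programming following the SAP text. Frequency is unknown and may be zero. The main safety endpoints, their Clopper-Pearson intervals and the sample-size statement are unaffected. An effect on Day 3 dose-normalised PK is conditional on the three points above and should not be asserted. Severity is low; the case for changing the text is that the correction is simple.

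**What to change.** Amend SAP 10.6 as follows:

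1. Assume the protocol durations only for infusions whose end-of-infusion status is completed as per protocol.
2. For all other infusions, keep every recorded time and impute only the missing element where the recorded times allow it. For example, place the rate change at 15 min when start and end are known.
3. If the recorded times do not determine the delivered volume, set actual dose and compliance for that infusion, and overall compliance, to missing. Flag and list the case.

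This follows the principle in SAP 10.5 for PK sample times, which are imputed only when compatible with the recorded parts. It would also help if SAP 7.8.3.1 stated whether its actual dose is the one computed in 5.5.2.

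The cost is one condition and a short programming change. No new data are needed, because the status is already planned for tabulation, and completed infusions are handled as now. The downside is that a few compliance values may be missing. For a subject whose other two infusions were complete, overall compliance can still be bounded between (100 + 100 + 0)/3 = 66.7% and 100%.

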11 CHANGES OR CLARIFICATIONS TO ANALYSES PLANNED IN THE STUDY PROTOCOL

This section describes changes to the statistical analysis planned in the protocol, and other deviations from the protocol relevant to the analysis or interpretation of the results.

11.1 Changes to the analyses planned in the study protocol

None.

11.2 Changes in the conduct of the study / data collection

None.

11.3 Clarifications concerning endpoint definitions and related variables or statistical methods

11.3.1 Treatment/period as factor in mixed model analysis

Protocol section 10.3.5 [D-17.055] states that the mixed model analysis of $C_{max, ss}$ and $AUC_{\tau, ss}$ contains terms for period, treatment and subject. Since 'period' and 'treatment' are confounded (Period 1: Uptravi, Period 2: i.v. Selexipag) only 'period' is used in the models.

11.3.2 Additional analyses as compared to the study protocol

- C_{trough} ratio of treatments per subject.
- Marked blood pressure abnormalities.

12 LIST OF TABLES, LISTINGS AND FIGURES

Since all tables, figures, and listings will be produced using SAS®, the outputs actually generated may slightly differ from the mock-ups presented in the study-specific mock-up catalogue.

12.1 Subject disposition

Output name	Display*	Title (Description)	Analysis set(s)**	Key deliverable	Mock layout
DISP	T	Subject disposition	SCR	Y	T_DISP
DISP_COU	T	Subject disposition by country and site	SCR		T_DISP_CO_U
ANA	T	Overview of analysis sets and reasons for exclusion from analysis sets	SCR		T_ANA
PWDS	T	Reasons for premature discontinuation from the study	SAF		T_PWDS

* T=Summary table, L=Listing, F=Figure, **SCR=Screened analysis set, SAF=Safety analysis set, ivSAF=i.v. Safety analysis set, PKS=Pharmacokinetic analysis set

12.2 Protocol deviations

Output name	Display*	Title (Description)	Analysis set(s)**	Key deliverable	Mock layout
PD	T	Summary of important protocol deviations	SCR		T_PD
PD_COU	T	Summary of all protocol deviations overall and by country	SCR		T_PD

* T=Summary table, L=Listing, F=Figure, **SCR=Screened analysis set, SAF=Safety analysis set, ivSAF=i.v. Safety analysis set, PKS=Pharmacokinetic analysis set

12.3 Subject characteristics

12.3.1 Demographics and baseline disease characteristics

Output name	Display*	Title (Description)	Analysis set(s)**	Key deliverable	Mock layout
DEM	T	Summary of baseline demographic characteristics	SAF	Y	T_DEM
AGECATE U	T	EudraCT age categories	SAF		T_AGEcate U
BAS	T	Summary of baseline disease characteristics	SAF	Y	T_BAS

* T=Summary table, L=Listing, F=Figure, **SCR=Screened analysis set, SAF=Safety analysis set, ivSAF=i.v. Safety analysis set, PKS=Pharmacokinetic analysis set

12.3.2 Other baseline characteristics

Output name	Display*	Title (Description)	Analysis set(s)**	Key deliverable	Mock layout
PHYS	L	Listing of physical examination results	SCR		L_PHYS

* T=Summary table, L=Listing, F=Figure, **SCR=Screened analysis set, SAF=Safety analysis set, ivSAF=i.v. Safety analysis set, PKS=Pharmacokinetic analysis set

12.3.3 Medical history

Output name	Display*	Title (Description)	Analysis set(s)**	Key deliverable	Mock layout
MH_PRV_SOC	T	Summary of previous diseases or diagnoses, by primary system organ class and preferred term	SAF		T_MH_SOC
MH_ONG_SOC	T	Summary of concomitant diseases or diagnoses, by primary system organ class and preferred term	SAF		T_MH_SOC

* T=Summary table, L=Listing, F=Figure, **SCR=Screened analysis set, SAF=Safety analysis set, ivSAF=i.v. Safety analysis set, PKS=Pharmacokinetic analysis set

12.3.4 Previous and concomitant medications

Output name	Display*	Title (Description)	Analysis set(s)**	Key deliverable	Mock layout
CM_PRV	T	Summary of previous therapies by Anatomical Therapeutic Chemistry (ATC) Class and Preferred Term [Add footnote: Previous therapies are therapies which ended prior to baseline.]	SAF		T_CM
CM_ONG	T	Summary of ongoing therapies by Anatomical Therapeutic Chemistry (ATC) Class and Preferred Term [Add footnote: Ongoing therapies are therapies which were started prior to baseline and are ongoing at study treatment start.]	SAF		T_CM
CM_CM	T	Summary of study concomitant therapies by Anatomical Therapeutic Chemistry (ATC) Class and Preferred Term [Add footnote: Study concomitant therapies are therapies which were started or dose changed (of those ongoing at baseline) during the respective period.]	SAF		T_CM
CM_ONG_PAH	T	Summary of ongoing PAH specific therapies at baseline [Add footnote: Ongoing therapies at study treatment start are therapies which were started prior to baseline and are ongoing at study treatment start.]	SAF	Y	T_CMPAH

* T=Summary table, L=Listing, F=Figure, **SCR=Screened analysis set, SAF=Safety analysis set, ivSAF=i.v. Safety analysis set, PKS=Pharmacokinetic analysis set

12.4 Study treatment exposure

12.4.1 Exposure

Output name	Display*	Title (Description)	Analysis set(s)**	Key deliverable	Mock layout
EXP_IV	T	Exposure to i.v. selexipag	ivSAF	Y	T_EXP_IV
EXP_PO	T	Exposure to Uptravi prior to and after i.v. selexipag	SAF ivSAF#		T_EXP_PO
COMPL_IV	T	Compliance to study treatment	ivSAF		T_COMPL_IV
EXP_ADJ	T	Summary of study treatment administration, reasons for interruptions and end of infusion	ivSAF		T_EXP_ADJ
EXP_SHF	F	Shift in selexipag dose between oral and i.v. treatment	ivSAF		F_EXP

* T=Summary table, L=Listing, F=Figure, **SCR=Screened analysis set, SAF=Safety analysis set, ivSAF=i.v. Safety analysis set, PKS=Pharmacokinetic analysis set, # Tables will run on SAF only if SAF and ivSAF are identical.

12.4.2 Study treatment discontinuation

Output name	Display*	Title (Description)	Analysis set(s)**	Key deliverable	Mock layout
PWDT	T	Reasons for premature discontinuation of i.v. selexipag treatment	ivSAF		T_PWDT

* T=Summary table, L=Listing, F=Figure, **SCR=Screened analysis set, SAF=Safety analysis set, ivSAF=i.v. Safety analysis set, PKS=Pharmacokinetic analysis set

12.5 Study withdrawal

See Section 12.4.

12.6 Primary efficacy analyses

Not applicable.

12.7 Safety analyses

12.7.1 Adverse events

Output name	Display*	Title (Description)	Analysis set(s)**	Key deliverable	Mock layout
AE_ALL_SOC	T	Incidence of adverse events by period, primary system organ class and preferred term	SAF ivSAF#	Y	T_AE_SOC
AE_INT	T	Incidence of adverse events by preferred term and maximum intensity	SAF ivSAF#		T_AE_PT_IN_T

* T=Summary table, L=Listing, F=Figure, **SCR=Screened analysis set, SAF=Safety analysis set, ivSAF=i.v. Safety analysis set, PKS=Pharmacokinetic analysis set, # Tables will run on SAF only if SAF and ivSAF are identical.

12.7.2 Deaths and serious adverse events

Output name	Display*	Title (Description)	Analysis set(s)**	Key deliverable	Mock layout
SAE_ALL_PT	T	Incidence of serious adverse events by period, and preferred term	SAF ivSAF#	Y	T_AE_PT
DTH	L	Listing of all deaths	SAF		L_DTH

* T=Summary table, L=Listing, F=Figure, **SCR=Screened analysis set, SAF=Safety analysis set, ivSAF=i.v. Safety analysis set, PKS=Pharmacokinetic analysis set, # Tables will run on SAF only if SAF and ivSAF are identical.

12.7.3 Prostacyclin-associated adverse events

Output name	Display*	Title (Description)	Analysis set(s)**	Key deliverable	Mock layout
AE_PC_PT	T	Incidence of prostacyclin-associated adverse events by period and preferred term	SAF ivSAF#	Y	T_AE_PT
SAE_PC_PT	T	Incidence of prostacyclin-associated serious adverse events by period and preferred term	SAF ivSAF#		T_AE_PT
AE_PCDC_PT	T	Incidence of prostacyclin-associated adverse events leading to discontinuation of study treatment by preferred term	SAF ivSAF#		T_AE_PT

* T=Summary table, L=Listing, F=Figure, **SCR=Screened analysis set, SAF=Safety analysis set, ivSAF=i.v. Safety analysis set, PKS=Pharmacokinetic analysis set, # Tables will run on SAF only if SAF and ivSAF are identical.

12.7.4 Adverse events of special interest based on the Uptravi risk management plan

Output name	Display*	Title (Description)	Analysis set(s)**	Key deliverable	Mock layout
AE_RMP	T	Incidence of adverse events of special interest based on the Uptravi risk management plan by period, risk category and preferred term [Replace SOC with Risk category in the Shell. Delete SOC on footnote regarding MedDRA version..]	SAF ivSAF#		T_AE_SOC
SAE_RMP	L	Listing of all serious adverse events of special interest based on the Uptravi risk management plan [Replace SOC with Risk category in the Shell.]	SAF ivSAF#		L_AE
AE_DC_RMP	T	Incidence of adverse events of special interest based on the Uptravi risk management plan leading to discontinuation of study treatment by period, risk category and preferred term [Replace SOC with Risk category in the Shell. Delete SOC on footnote regarding MedDRA version.]	SAF ivSAF#		T_AE_SOC

* T=Summary table, L=Listing, F=Figure, **SCR=Screened analysis set, SAF=Safety analysis set, ivSAF=i.v. Safety analysis set, PKS=Pharmacokinetic analysis set, # Tables will run on SAF only if SAF and ivSAF are identical.

12.7.5 Injection site reaction adverse events

Output name	Display*	Title (Description)	Analysis set(s)**	Key deliverable	Mock layout
AE_INJ_IN_T	T	Incidence of clinically significant injection site reaction adverse events by preferred term and maximum intensity	ivSAF	Y	T_AE_PT_IN_T
AE_INJDE_T	T	Grade and diagnosis criteria of injection site reactions	ivSAF		T_AEINJ

* T=Summary table, L=Listing, F=Figure, **SCR=Screened analysis set, SAF=Safety analysis set, ivSAF=i.v. Safety analysis set, PKS=Pharmacokinetic analysis set.

12.7.6 PAH-related adverse events

Output name	Display*	Title (Description)	Analysis set(s)**	Key deliverable	Mock layout
AE_PAH_PT	T	Incidence of PAH related adverse events by period and by preferred term	SAF ivSAF#		T_AE_PT

* T=Summary table, L=Listing, F=Figure, **SCR=Screened analysis set, SAF=Safety analysis set, ivSAF=i.v. Safety analysis set, PKS=Pharmacokinetic analysis set, # Tables will run on SAF only if SAF and ivSAF are identical.

12.7.7 Adverse events leading to study treatment discontinuation

Output name	Display*	Title (Description)	Analysis set(s)**	Key deliverable	Mock layout
AE_DC_PT	T	Adverse events leading to discontinuation of study treatment by preferred term	ivSAF		T_AE_PT

* T=Summary table, L=Listing, F=Figure, **SCR=Screened analysis set, SAF=Safety analysis set, ivSAF=i.v. Safety analysis set, PKS=Pharmacokinetic analysis set.

12.7.8 Adverse events related to study drug

Output name	Display*	Title (Description)	Analysis set(s)**	Key deliverable	Mock layout
AE_REL_PT	T	Incidence of adverse events related to study treatment as judged by the investigator by period and by preferred term	ivSAF		T_AE_PT

* T=Summary table, L=Listing, F=Figure, **SCR=Screened analysis set, SAF=Safety analysis set, ivSAF=i.v. Safety analysis set, PKS=Pharmacokinetic analysis set.

12.7.9 Summaries of adverse events for disclosure

Output name	Display*	Title (Description)	Analysis set(s)**	Key deliverable	Mock layout
SAE_CTGOV	T	Summary of treatment emergent SAEs	SAF		T_AE_SOC2
SAE_REL_CTGOV	T	Summary of treatment emergent SAEs judged to be treatment related by the investigator	SAF		T_AE_SOC2
SAE_DTH_CTGOV	T	Summary of treatment emergent SAEs with fatal outcome	SAF		T_AE_SOC2
SAE_DTH_REL_CTGOV	T	Summary of treatment emergent SAEs with fatal outcome judged to be treatment related by the investigator	SAF		T_AE_SOC2
NSAE_5PC_T_CTGOV	T	Summary of non-serious AEs with an incidence of 5% or higher in any treatment group	SAF		T_AE_SOC2

* T=Summary table, L=Listing, F=Figure, **SCR=Screened analysis set, SAF=Safety analysis set, ivSAF=i.v. Safety analysis set, PKS=Pharmacokinetic analysis set

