9 SAFETY DEFINITIONS AND REPORTING REQUIREMENTS

9.1 Adverse events

9.1.1 Definition of adverse events

An AE is any untoward medical occurrence, i.e., any unfavorable and unintended sign, including an abnormal laboratory finding, symptom, or disease that occurs in a subject during the course of the study, whether or not considered by the investigator as related to study treatment.

A treatment-emergent AE is any AE temporally associated with the use of i.v. selexipag; from start of first i.v. selexipag infusion until 30 days after end of last i.v. selexipag infusion (i.e., Period 2, and Period 3 and follow-up Period combined); whether or not considered by the investigator as related to study treatment.

AEs include:

- Exacerbation of a pre-existing disease.
- Increase in frequency or intensity of a pre-existing episodic disease or medical condition.
- Disease or medical condition detected or diagnosed during the course of the study even though it may have been present prior to the start of the study.

- Continuous persistent disease or symptoms present at study start that worsen following the signing of informed consent.
- Abnormal assessments, e.g., change on physical examination, ECG findings, if they represent a clinically significant finding that was not present at study start or worsened during the course of the study.
- Laboratory test abnormalities if they represent a clinically significant finding, symptomatic or not, which was not present at study start or worsened during the course of the study or led to dose reduction, interruption or permanent discontinuation of study treatment.

Overdose, misuse, abuse of the study treatment (i.v. selexipag) and study treatment errors will be reported as an AE.

Overdose is defined as any infused dose of selexipag greater than the dose corresponding to 1600 µg b.i.d. of Uptravi.

Study treatment errors include medication error (e.g., any infused dose of selexipag greater than the individual corresponding prescribed dose of Uptravi) and administration errors (e.g., incorrect infusion rate).

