10.1.2 Full Analysis Set

Not applicable.

10.1.3 i.v. Safety Set

The i.v. Safety Set comprises all subjects who received at least one dose of i.v. study treatment.

The i.v. Safety Set will be used to capture safety and tolerability for all subjects who had at least one dose of i.v. selexipag.

All analyses for Periods 2 and 3 combined, and for Period 2 separately will be carried out on the i.v. Safety Set.

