10.1.6 Usage of the analysis sets

Subject disposition is described for the Screened Analysis Set. Demographics and baseline characteristics will be reported on the SAF. Safety analyses will be carried out on the SAF and on the i.v. Safety Set. PK analyses will be carried out on the PKS. Subject listings are based on the SAF or Screened Analysis Set as applicable. The following table describes the use of the analysis sets.

Table 4 Reporting periods and corresponding analysis sets.

Reporting period(s)*	Variables	Analysis set
Period 1	Safety and tolerability	SAF
Period 2	Safety and tolerability	i.v. Safety Set
Period 3	Safety and tolerability	i.v. Safety Set
Period 1 and 2	Safety and tolerability	SAF
Period 2 and 3	Safety and tolerability	i.v. Safety Set
Period 1 and 2 and 3	Safety and tolerability	SAF
Period 1 and 2	Pharmacokinetic	SAF, PKS

Follow-up period will be reported together with Period 3.

* If a subject does not take at least one dose of selexipag i.v. they will not be considered as having entered Period 2 (or 3).

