2.5 Sample Size

No confirmatory statistical tests are planned in the study.

Approximately 20 subjects will be enrolled to have at least 18 subjects in the i.v. Safety Set. In the GRIPHON Phase 3 pivotal study of selexipag, a proportion of 7.5% of subjects prematurely discontinued the study (i.e., without a morbidity/mortality event) due to prostacyclin-associated adverse events (AEs) across the titration and maintenance phases. It is expected that the proportion of early discontinuations during the entire study will not be higher than 10% (i.e., that approximately 18 subjects will enter the i.v. period).

A sample size of 18 subjects in the i.v. Safety Analysis Set will ensure that, if the true rate of discontinuations due to prostacyclin-associated AEs is between 5% and 10%, the half-width of the 95% confidence interval (CI) will be below 35%.

The precision achieved with a sample size of approximately 18 subjects in the i.v. Safety Set is considered adequate for this study (e.g., the upper boundary of the CI for the i.v. Safety Analysis Set excludes values above 35%, and for the Safety Analysis Set, above 32%).

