4.1.3 Safety Analysis Set

The Safety Analysis Set (SAF) includes all enrolled (included in the study on Day 1) subjects who received at least one dose of Uptravi or i.v. selexipag during any of Period 1, Period 2, or Period 3 of the study.

4.1.4 i.v. Safety Analysis Set

The i.v. Safety Analysis Set (ivSAF) includes all subjects who received at least one dose of i.v. selexipag.

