7.2 Adverse events

7.2.1 Variables

The original verbatim terms used by investigators to identify AEs in the eCRF will be mapped to PTs using the MedDRA dictionary using the latest version at data cutoff. The AE PTs will be then grouped by MedDRA PTs into frequency tables according to primary SOC.

7.2.1.1 *Treatment-emergent adverse events*

The analysis of AEs in Period 2, Period 3 and safety follow-up period is considered analysis of treatment-emergent events, as the i.v. formulation is the investigational treatment.

7.2.1.2 *Adverse events related to study treatment*

An AE will be considered related to the study treatment if the investigator answered 'yes' to the question 'Causal relationship to i.v. selexipag' or if it is missing.

7.2.1.3 *Serious adverse events*

An AE will be considered serious if the investigator answered 'Yes' to the question 'Serious?' or if information is missing.

7.2.1.4 *Adverse events leading to discontinuation of study treatment*

An AE is considered as leading to discontinuation of study treatment if the investigator ticked 'Drug withdrawn' on the question 'Action taken with study treatment'.

7.2.1.5 *Injection site reactions*

Injection site reactions will be collected on a separate eCRF page. Clinically significant injection site reactions will be reported as an AE.

7.2.1.6 *Prostacyclin-associated AEs*

Prostacyclin-associated AEs are AEs associated with the pharmacological action of selexipag that have been observed frequently, in particular during the phase of individualized dose titration. According to selexipag Investigator's Brochure (IB) reference safety information, these PTs include headache, diarrhea, nausea, vomiting, jaw pain, myalgia, pain in the extremity, flushing, and arthralgia.

7.2.1.7 *AEs of special interest based on the Utravi Risk Management Plan*

For completeness, AEs will be analyzed according to the Utravi Risk Management Plan (RMP) important identified or potential risks, using searches of MedDRA PTs provided by Global Drug Safety at the time of database closure. In accordance with the RMP, the following categories will be analyzed:

- Hypotension
- Anemia, decrease in hemoglobin concentration

- Hyperthyroidism
- Major adverse cardiovascular events
- Acute renal failure
- Bleeding events
- Light-dependent non-melanoma skin tumors
- Ophthalmological effects associated to retinal vascular system

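### SAP 12.7.9 puts the four treatment-emergent SAE disclosure tables on the SAF, although the protocol and the rest of the SAP assign that window to the i.v. Safety Set

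*SAP*

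**What the plan says.** SAP 12.7.9 lists five outputs for registry disclosure, all with SAF as the analysis set. Four have treatment-emergent in the title, beginning with "Summary of treatment emergent SAEs". The fifth covers non-serious AEs at 5% incidence or more, and its title does not say treatment-emergent. None carries the # footnote, under which most other AE tables are run on SAF and ivSAF, or on SAF alone if the two sets are identical.

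The two sets differ by definition:

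- SAP 4.1.3: the SAF takes in enrolled "subjects who received at least one dose of Uptravi or i.v. selexipag during any of Period 1, Period 2, or Period 3" of the study, so an oral dose is enough.
- SAP 4.1.4: "The i.v. Safety Analysis Set (ivSAF) includes all subjects who received at least one dose of i.v. selexipag".

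Treatment-emergent is tied to the infusion:

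- Protocol 9.1.1 runs the window "from start of first i.v. selexipag infusion until 30 days after end of last i.v. selexipag infusion".
- SAP 7.2.1.1: "The analysis of AEs in Period 2, Period 3 and safety follow-up period is considered analysis of treatment-emergent events".

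The set for that window is fixed in protocol 10.1.3: "All analyses for Periods 2 and 3 combined, and for Period 2 separately will be carried out on the i.v. Safety Set". Protocol Table 4 and SAP Tables 4 and 7 agree. SAP 11.1 declares no change to the analyses planned in the protocol.

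**The concern.** A percentage of treatment-emergent events needs a denominator of subjects who could have had one. The footnote to protocol Table 4 says that a subject without an i.v. dose does not count as having entered Period 2 or Period 3. Such a subject can be in the SAF through the Day 1 oral dose, but can never contribute to the numerator of these tables.

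At stake is the agreement between two public sources. SAP 7.2.2.1 says that these outputs serve EudraCT and ClinicalTrials.gov and not the study report. If the sets differ, the registries would show lower percentages than the report's tables for Period 2, 3 and follow-up combined, from the same events.

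**Working it through.** **Inputs**

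- Planned sizes (SAP 2.5): "Approximately 20 subjects will be enrolled to have at least 18 subjects in the i.v. Safety Set".
- Early discontinuations expected at no more than 10% (SAP 2.5).
- Upper 95% limits said to exclude values above 35% (ivSAF) and 32% (SAF) (SAP 2.5).
- Exact Clopper-Pearson intervals (SAP 7.2.2).
- Enrolment limits (SAP 2.1): Group A 5 to 8, Group B 12 to 15.

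**Step 1: the plan's own figures.** 20 × (1 − 0.10) = 18. With two events, the exact 95% upper limit is 34.7% for 2/18 and 31.7% for 2/20, which match the stated 35% and 32%. The sample size section therefore already works with an SAF of 20 and an ivSAF of 18; it does not take the sets to be equal.

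**Step 2: the dilution factor.** For x subjects with an event, the SAF rate divided by the ivSAF rate is (x / n_SAF) ÷ (x / n_ivSAF) = n_ivSAF / n_SAF. It does not depend on x.

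| Non-infused subjects among 20 | Factor |
|---|---|
| 0 | 20/20 = 1.00 |
| 1 | 19/20 = 0.95 |
| 2 (planned) | 18/20 = 0.90 |

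**Step 3: percentages at the planned sizes.**

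| Subjects with event | SAF, n = 20 | ivSAF, n = 18 |
|---|---|---|
| 1 | 5.0% | 5.6% |
| 2 | 10.0% | 11.1% |
| 3 | 15.0% | 16.7% |

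**Step 4: dose-group columns.** The shell for these outputs, T_AE_SOC2, has one column per dose group. The documents do not say how many subjects per group would go without an infusion. Assuming that both non-infused subjects fall in the same group:

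| Group, enrolled | Factor | One subject with event: SAF, ivSAF |
|---|---|---|
| A, 5 | 3/5 = 0.60 | 20.0%, 33.3% |
| A, 8 | 6/8 = 0.75 | 12.5%, 16.7% |
| B, 12 | 10/12 = 0.83 | 8.3%, 10.0% |
| B, 15 | 13/15 = 0.87 | 6.7%, 7.7% |

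**Step 5: the 5% cut-off of the fifth output.** One subject in the largest possible group is 1/15 = 6.7%, already above 5%. With either denominator, any term reported by one subject in a dose group is listed. The choice of set changes the printed percentage, not which terms appear.

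**The case against.** Four arguments can be made for leaving the tables alone.

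1. **The harm may be nil.** A reader might infer that the registry figures will be too low and will not match the report. The documents do not support that as a certainty. SAP Tables 4 and 7 provide for identical sets, and then the effect is zero. The 10% is an upper expectation, drawn from a study whose rate covered titration and maintenance. Here a subject would have to drop out between the Day 1 oral dose, on a regimen stable for at least 28 days, and the first infusion the next morning. This stands: the dilution must be stated as conditional.

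2. **The protocol also allows the SAF.** Protocol 10.3.4 has AEs and SAEs tabulated for both sets, overall and by period, and SAP 12.7.2 lists the SAE table for both. That permits the SAF alongside the i.v. set. It does not override the specific rule in protocol 10.1.3 for Periods 2 and 3, and it does not explain why 12.7.9 names the SAF alone.

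3. **The denominator rule may already exclude non-infused subjects.** SAP 8.1.1 bases percentages on the relevant analysis set and period. Read with the footnote to protocol Table 4, this would drop anyone who never entered Period 2. The reading is possible but not secured: T_AE_SOC2 has no period line and shows one N per dose group, and SAP 7.2.2.1 names no denominator.

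4. **The fifth output is not clearly treatment-emergent.** SAP 7.2.1.9 defines a non-serious AE as any AE marked not serious, without a time window. Only the lead-in of SAP 7.2.2.1 suggests treatment-emergent scope. Restricting this table to Period 2 onward could remove Period 1 events that were meant to be shown. This stands, and its scope must be settled before its set is changed.

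**Conclusion.** SAP 12.7.9 conflicts with protocol 10.1.3, protocol Table 4 and SAP Tables 4 and 7 for the four treatment-emergent SAE outputs. That conflict does not depend on the data. No reason for the SAF is given, and the neighbouring tables of treatment-related AEs (12.7.8) and of AEs leading to discontinuation (12.7.7) use ivSAF.

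The numerical effect arises only if at least one SAF subject receives no infusion. At the planned sizes it is 10% in relative terms, or 0.6 percentage points for one subject with an event. The Group A factors of 0.60 to 0.75 rest on the assumption that both non-infused subjects are in that group, and should not be read as expected values. A table with no events reads 0% either way. Subject and event counts are unchanged, the study report tables are not touched, and the shell prints the denominator. This is a minor inconsistency, worth correcting because the correction costs almost nothing.

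**What to change.** - In SAP 12.7.9, change the analysis set of the four treatment-emergent SAE outputs from SAF to ivSAF, or list both with the # footnote used in 12.7.1 to 12.7.4.
- Add a footnote to T_AE_SOC2 giving the denominator and the period (Period 2, Period 3 and safety follow-up combined).
- For the non-serious AE output, first confirm whether it is treatment-emergent, as the lead-in of SAP 7.2.2.1 implies. If so, say so in the title and use ivSAF. If not, state the period that it covers and keep a set that fits it.

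For the four SAE outputs the cost is one column entry each and a shared footnote. The fifth needs a short decision on scope. No new data are needed, and if the two sets turn out identical the four SAE tables come out the same.
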